2.3 Hypotheses and Specific Aims

Hypothesis I

Bone grafted sites preserve alveolar ridge dimensions of extraction sockets more effectively than extraction sites that have healed without grafting.

Specific Aims

- 1: Compare alveolar ridge dimensions in grafted extraction sockets to that of sites healed without grafts after 8 weeks of post-extraction healing.

Hypothesis II

The addition of growth factors to bone grafting materials will enhance osseous and soft-tissue healing.

Specific Aims

- 2: Assess the efficacy of bone grafting with and without enrichment with growth factors to preserve the volume of bone in extraction sockets.

- 3: Compare soft tissue healing between groups at week-1, week-2, week-4 and after 8 weeks of post-extraction healing

- 4: Assess quantitative bone fill across groups after 2 months of post-extraction healing
- 5: Compare qualitative bone fill across groups after 2 months of post-extraction healing.
- 6: Assess and compare the relationship of osseous healing and implant stability at insertion across groups after 2 months of post-extraction healing.

Hypothesis III

Laser Thread Textured (LTT) dental implant will help preserve longitudinal peri-implant crestal bone more effectively than implants with Resorbable Blast Texturing (RBT).

Specific Aims

- 7: Assess the efficacy of LTT and RBT surface topographies when surgically implanted into extraction sockets.
- 8: Assess peri-implant soft-tissue healing adjacent to LTT and RBT surfaced implants.
- 9: Assess changes in longitudinal crestal bone level across extraction groups and between implant groups at 12 and 24 months after surgical implant placement.

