4.9 Post-Extraction Evaluations

Participants will return to clinic for oral evaluations as close to 7-days after the extraction/grafting procedure as possible and again at 14 days; sutures will be removed at the 14-day visit. An additional follow-up visit will be scheduled approximately 1-month following extractions. Healing will be closely monitored and appropriate data recorded on follow-up CRFs.

At each visit, medical history will be reviewed and any changes documented. Information regarding adverse events will be captured and recorded following IRB and Federal reporting guidelines. Eight weeks after the extractions, each study subject will be appointed for a second CBCT scan, a bone-fill biopsy and surgical placement of implants.

Table 2 – Study Procedures Visits -1 — 8

Procedures	V- (-1) Screening	V-1 Pre-Tx	V-2 EXT/ G	V-3 Week 1	V-4 Week 2	V-5 Week 4	V-6 Week 8 implant s	V-7 Week 10	V-8 Expose Implant
Consent Discussion/Obtained	X								
Medical History Review		X	X	X	X	X	X	X	X
Tx Plan Review		X							
Impressions		X							
Essix Retainer		X							
Randomized to Tx Groups		X							
Biopsy site selection		X							
Pre-Surg Antibiotics			X				X		
Pre-Surg Oral Rinse			X				X		
Tooth Extraction			X						
Tx Group Procedure			X						
Venipuncture (group 3 only)			X						
Clinical Photographs			X	X	X	X	X		X
CBCT Scan			X				X		
Periapical Radiographs							X		X
Post-Surg Instructions/Prescriptions			X				X		X
Suture Removal				X					X
AE's recorded			X	X	X	X	X	X	X
Bone Biopsy							X		
Implant Placement							X		
Implant Exposure									X

Table 3 Study Procedures Visits 9 —12

Procedures	V-9 Impressions	V-10 Final Restoration	V-11 12 month	V-12 24 month
Medical History Review	X	X	X	X
Impressions	X			
Clinical Photographs	X	X	X	X
Final Restoration Attached		X		
Periapical Radiographs		X	X	X
AE's recorded	X	X	X	X
Soft-tissue assessments			X	X
Pocket Depth Measurements			X	X
Patient Satisfaction			X	X

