6.0 RESTORATION OF IMPLANTS

6.1 Implants Uncovered

Implants will be uncovered upon the investigator's determination that the implants are sufficiently integrated to withstand the forces of loading. In general, mandibular implants will be uncovered and restoration initiated approximately 4 months after placement; maxillary implants will be uncovered and restoration initiated approximately 6 months after placement. When the implants are uncovered, clinical photographs will be taken before, during and after the procedure; following the procedure, standardized intra-oral radiographs of each implant site will be made.

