6.2 Placement of the final restoration

Each implant will be restored in the conventional manner with an aesthetically pleasing single crown restoration. Restoring materials will be selected by the restoring dentist based on discretion of the dentist and individual patient needs. Prosthetic restoration of the implants will require numerous visits to the restorative dentist over a period of one to two-months. The restoring dentist will advise when additional visits are necessary. Photographs will document each step in the restoration process and of radiographs be taken of each area when the final restoration is cemented.

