This SA will be addressed using a survival analysis approach. The primary outcome measure will be presence of signs and symptoms of infection at the implant site, since implant failure is expected to be rare to non-existent. Frequencies of occurrence of infection will be tabulated for each implant type.

Cox proportional hazards regression will be used to evaluate the rates of infection for LTT and RBT implants, allowing for adjustment for potential confounding variables and covariates. A blocking variable representing the individual subject will be included in order to reflect multiple implants per study subject.

SA-8: Assess peri-implant soft tissue healing adjacent to LTT and RBT surfaced implants

The JEMPT index will be evaluated at the time of final restoration and at 12 and 24 months follow-up evaluations. Mixed model ANOVA will be used to compare changes over time between implant types. The statistical test that will be of primary interest is the implant type by time interaction.

SA-9: Assess changes in the longitudinal crestal bone levels across extraction groups and between implant groups at 12 and 24 months after surgical placement.

The analysis for the SA will be mixed-model ANOVA, accounting for multiple observations per subject. The statistical test that will be of primary interest is the F-test for surface type by time interaction.

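### SA-8's lead test, collar type by time from final restoration, cannot detect a collar difference already present at restoration, and SA-9 does not state the response and time levels on which its interaction test depends

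*Combined protocol and SAP*

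**What the plan says.** **SA-8.** Aim 8 in Section 2.3 reads: "Assess peri-implant soft-tissue healing adjacent to LTT and RBT surfaced implants". Section 12.4 gives the visits: "The JEMPT index will be evaluated at the time of final restoration and at 12 and 24 months follow-up evaluations". It gives the method, "Mixed model ANOVA will be used to compare changes over time between implant types", and the lead test, "The statistical test that will be of primary interest is the implant type by time interaction".

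**Timing of restoration.** Section 6.1 says "mandibular implants will be uncovered and restoration initiated approximately 4 months after placement" and "maxillary implants will be uncovered and restoration initiated approximately 6 months after placement". Section 6.2 adds: "Prosthetic restoration of the implants will require numerous visits to the restorative dentist over a period of one to two-months".

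**Follow-up of interactions.** The general text of Section 12.4 plans least-squares-mean plots and separate time-point analyses for interactions that are significant. It names no collar comparison for SA-8 or SA-9 apart from the interaction.

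**SA-9.** The lead test is surface type by time. Section 12.4 does not say whether the response is bone level or change in bone level, or which visits are levels of time. Section 12.3 compares 12- and 24-month bone heights with insertion and derives changes from baseline. Section 12.1 mentions only the 12- and 24-month radiographs for image analysis. The opening of Section 12.0 says data are captured at placement as well, and Section 8.2 schedules a radiograph at placement.

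**Power.** Section 12.5 bases SA-8 and SA-9 on a t-test between the two implant types: 70% power for 0.50sd and 80% for 0.565sd, where sd is that of changes across time.

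**Schedule.** Table 3 (Section 4.9) marks "Soft-tissue assessments" at 12 and 24 months but not at the final-restoration visit.

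**The concern.** A group-by-time interaction asks whether the group difference changes between the visits in the model. It answers the treatment question when the first visit precedes treatment. In SA-8 the first visit follows months of healing next to the randomised collar, which is what the aim sets out to assess. If the collars differ by restoration and the difference persists, the lead test is expected to be null, and no planned analysis then reports the difference.

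In SA-9, the only one of the three aims under Hypothesis III that is analysed on crestal bone, the same loss occurs under one of two readings of the model. The documents do not say when a collar difference would arise, so the power of the lead tests cannot be taken for granted.

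**Working it through.** **Inputs.** Effective n is 50 per collar (Section 12.5, stated under SA-7). Testing is two-sided at 5%, and a medium effect is 0.50sd (Section 12.5). The documents give no correlation between visits. I assume compound symmetry with ρ from 0.5 to 0.8.

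**Step 1: the plan's own figure.** For a two-group t-test the noncentrality is d√(n/2).
- d = 0.5: 0.5 × √25 = 2.5 on 98 df, power 69.7% (plan: 70%).
- d = 0.565: 2.825, power 79.9% (plan: 80%).
- With 25 per group, 0.5sd would have only 41%, so 50 per collar is the n behind Section 12.5.

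**Step 2: when restoration occurs.** Mandible: 4 + 1 to 4 + 2 = 5 to 6 months after placement. Maxilla: 6 + 1 to 6 + 2 = 7 to 8 months.

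**Step 3: SA-8 interaction.** With collar differences d_j at k visits and score sd σ,

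λ = (n/2) Σ(d_j − d̄)² / [σ²(1 − ρ)], on k − 1 and (k − 1)(2n − 2) df, here 2 and 196.

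If all d_j are equal, the sum is zero, λ = 0 and power is 5% whatever the difference. For d = (0, 0.5, 0.5) the sum is 1/6, so λ = 25 × (1/6)/0.5 = 8.33 at ρ = 0.5 and 20.83 at ρ = 0.8. In units of σ:

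| Difference at restoration, 12, 24 months | λ (ρ = 0.5; 0.8) | Interaction | t-test on change, restoration to 24 months | 24-month contrast |
|---|---|---|---|---|
| 0.5, 0.5, 0.5 | 0; 0 | 5% | 5% | 70% |
| 0.25, 0.5, 0.5 | 2.08; 5.21 | 23-51% | 24-50% | 70% |
| 0, 0.5, 0.5 | 8.33; 20.83 | 73-99% | 70-97% | 70% |
| 0, 0.5, 0.25 (fades) | 6.25; 15.63 | 60-95% | 24-50% | 24% |

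Simulation of 20,000 trials per setting agreed for the first three rows (interaction 4.9-5.0%, 22.9-51.4%, 73.1-98.6%). The 70% for the contrast becomes 68-73% at 48 to 53.5 per collar, which are half of Section 12.5's effective totals of 96 and 107.

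The collar main effect averaged over the three visits has sd √[(1 + 2ρ)/3]. For a constant 0.5sd, its noncentrality is 3.06 (ρ = 0.5) or 2.69 (ρ = 0.8), which gives 86% or 76%. For (0, 0.5, 0.5) the mean difference is 1/3, the noncentrality is 2.04 or 1.79, and power is 52% or 43%.

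**Step 4: SA-8 in Section 12.5's unit.** Setting the sd of change to 1 means 2σ²(1 − ρ) = 1, so σ²(1 − ρ) = 0.5.
- Differences in change of 0.5 at both follow-ups: λ = 8.33, power 73%.
- 0.25 then 0.5: the sum is 0.125, λ = 6.25, power 60%.

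These are near the plan's 70%, but only for differences that arise after restoration.

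**Step 5: SA-9, in sd of change from insertion.** With insertion as a time level, use the formula in Step 3 with d = 0 at insertion. On derived changes at 12 and 24 months only, the test is a t-test on d₂₄ − d₁₂ with sd √[2(1 − ρ)], where ρ is now the correlation between the two changes. For example, 0.25/1 × 5 = 1.25 gives 24%, and 0.25/0.632 × 5 = 1.98 gives 50%.

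| Difference in change at 12, 24 months | Insertion as a time level | Derived changes only | 24-month contrast in change |
|---|---|---|---|
| 0.5, 0.5 | 73% | 5% | 70% |
| 0.25, 0.5 | 60% | 24-50% | 70% |
| 0, 0.5 | 73% | 70-97% | 70% |
| 0.5, 0.25 (fades) | 60% | 24-50% | 24% |

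**The case against.** **SA-8 is coherent as a question about change.** The method sentence, the lead test and the power unit all refer to change over time. A reader might infer that Section 12.5 powered a different test from the one planned. For SA-8 that is not supported: a t-test on change from restoration is one component of the same interaction. It gives similar power and shares the blind spot. This part of the objection stands.

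**A 24-month contrast changes the estimand and does not always win.** This also stands. Three of the four rows in the SA-8 table fix the difference at 0.5sd at 24 months, so the contrast has 70% in those rows by construction. A reader might infer that the interaction must be replaced outright. The documents do not settle when an effect arises, and the interaction does better for late or fading effects.

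**SA-9 may be sound as intended.** A reader might infer that its lead test is wrong. Sections 12.0 and 8.2 support placement as a time level, and on that reading the interaction is appropriate. What stands against the plan is that Sections 12.1 and 12.3 allow the other reading and Section 12.4 does not choose.

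**Table 3 does not prove that the restoration score is missing.** Section 8.4 and Table 3 both place photographs at final restoration, and the documents do not say how the index is scored. That is a conflict to reconcile, and I do not rest the conclusion on it.

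**Section 12.3 promises that group differences will be calculated.** It does, but it names no test, visit or model, so it does not fill the gap in Section 12.4.

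**Conclusion.** The SA-8 point holds without any assumption about correlation or effect size: a collar difference present at restoration and constant afterwards leaves the lead test at its 5% error rate. No collar contrast is named, and time-point analyses follow only a significant interaction. With half of a 0.5sd difference present at restoration, power is 23-51%. These partial figures rest on 50 per collar, compound symmetry and an assumed correlation of 0.5-0.8. Section 12.5's 70% for SA-8, with change taken from restoration, describes later-arising differences only.

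The SA-9 point is conditional. With insertion as a time level, power is 60-73% and close to the plan's figure. On derived changes at 12 and 24 months alone, it is 5% for a benefit complete by 12 months, where Section 12.5 states 70%. The wording should be settled before analysis. The plan is not shown to be unable to address Hypothesis III.

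**What to change.** **SA-9.** State that the response is change in bone level from insertion. Make the collar contrast in change at 24 months the lead test, which is the t-test that Section 12.5 powers, and keep surface by time as a named secondary. Alternatively, keep the interaction as lead and state that insertion is a time level in the model.

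**SA-8.** Pre-specify a collar comparison of the index, either at 24 months or as the main effect over visits, to be tested and reported whatever the interaction shows. Keep type by time as a named test and say which one leads. State that Section 12.5's figures for SA-8 refer to change after restoration. Reconcile the restoration-visit score in Section 12.4 with Table 3.

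**Cost.** Only SAP wording changes. The 24-month index and radiograph are already scheduled, and because collar is randomised, a comparison of levels needs no pre-treatment score. The price is power in some patterns. The 24-month SA-8 contrast has 70% against the interaction's 73-99% if the difference arises only after restoration, and 24% against 60-95% if it fades to 0.25sd by 24 months. That is why the interaction should stay as a named test.

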5.6 Implant Placement

The sterile blister pack containing the implant will drop onto a sterile field and after thorough irrigation of the site the implant will be inserted directly into the prepared bone site. After placement with the collar 1mm above the bone the insertion torque will be measured with a torque wrench and recorded on the case report forms. A cover cap will be placed on the implant and the surgical wound sutured.

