5.7 Immediate Post-Operative Procedures

Standardized intra-oral periapical dental radiographs will be made of each study site. Written and verbal post-operative instruction will be provided to each participant. An antimicrobial mouth rinse and ice packs will be dispensed. Antibiotics will be prescribed for 7 days; analgesics will be prescribed on an as needed basis at the discretion of the surgeon.

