8.2 Intra-oral radiographs

Standardized intra-oral periapical radiographs will be obtained of each site when the implants are placed and uncovered, at final implant restoration and at twelve and twenty-four months after the implants are placed. A minimum of five radiographs per study site over the duration of the study will be obtained. Additional radiographs may be obtained based on the study dentist's determination of need.

Radiographs will be used to monitor osseous health at the bone-implant interface, to verify implant position, to assess the quality of implant-attachment interface and to capture measurements of longitudinal osseous support to the implants.

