12.3 Outcome Endpoints

The primary efficacy parameter for implant success will be the duration of implant survival from surgical placement to 24 months post-placement across all groups. Measurement of bone height along the implant mesial and distal surfaces at 12 and 24 month follow-up evaluations will be captured from radiographic images and compared to same measurements at insertion. These measurements will be used to derive changes from baseline values.

Efficacy endpoints will include implant and prosthesis function as assessed by gingival health, bone levels and participant subjective satisfaction with the study therapy. Differences between groups will be calculated and used to determine if osseous changes and implant function are different across extraction groups and between implant groups.

Safety will be evaluated by clinical signs and symptoms of dental and medical events.

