Power estimation for the comparison of bone height measurements (SA-7), for comparison of changes in JEMT index (SA-8) and of changes in crestal bone levels (SA-9) between the two implant types was based on a t-test. The proposed sample size would provide 70% power to detect a medium effect size, and 80% power to detect a difference of 0.565sd between the groups. For SA-8 and SA-9, sd refers to the within-group standard deviation of changes across time.

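### SA-9 compares collars on change in crestal bone without adjusting for the insertion reading already taken at every implant, forgoing precision of uncertain size; its named test must change for adjustment to help.

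*Combined protocol and SAP*

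**What the plan says.** Section 12.3 takes mesial and distal bone height at 12 and 24 months; these "will be captured from radiographic images and compared to same measurements at insertion", and "These measurements will be used to derive changes from baseline values".

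The insertion film exists for every site. Section 5.7, on the immediate post-operative period, states "Standardized intra-oral periapical dental radiographs will be made of each study site". Section 8.2 repeats it: "Standardized intra-oral periapical radiographs will be obtained of each site when the implants are placed and uncovered".

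For SA-9, section 12.4 says "The analysis for the SA will be mixed-model ANOVA, accounting for multiple observations per subject", and then "The statistical test that will be of primary interest is the F-test for surface type by time interaction". It does not list the levels of time. Smoking status is the only covariate that 12.4 names for all models. Wider covariate adjustment is mentioned only for the Cox model under SA-7. SA-9 covers two comparisons, one across extraction groups and one between collars.

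Section 12.5 bases SA-9 power on a t-test between the two collars: 70% power at 0.50 sd, and 80% power at 0.565 sd. It adds "For SA-8 and SA-9, sd refers to the within-group standard deviation of changes across time".

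**The concern.** Subtracting the insertion reading from the follow-up reading fixes the slope on insertion at 1. If the true slope is different, part of the chance variation in the insertion reading (placement depth around the target, film geometry) stays in the change score as noise. Estimating the slope removes that noise and is never less efficient in large samples.

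The collar is randomised and the film is taken straight after placement, before the collar can have affected the crest. For the collar comparison the reading is therefore a legitimate baseline covariate that is already being collected.

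SA-9 is the aim that addresses crestal bone under Hypothesis III, and it is planned below 80% power. Even 70% is not a cautious figure. Section 12.5's own case of 1.5 sites per participant gives 96 effective observations, or 48 per collar, for which power is 67.9%.

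**Working it through.** **Inputs from the documents (12.5).** Two-sided 5% test; difference 0.50 sd, where sd is the SD of change; t-test between collars. The effective size of 50 per collar is stated for SA-7, and the same size reproduces the SA-9 figures.

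**Inputs not in the documents (assumed, shown over a range).** rho, the correlation of insertion and follow-up readings; lambda, the insertion SD divided by the follow-up SD.

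**Step 1: the plan's figure.** Noncentrality = 0.50 × √(50/2) = 2.5 on 98 df. Power is 69.7%, against 70% stated. The difference detectable with 80% power is 0.566 sd, against 0.565 stated. Both reproduce.

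**Step 2: variance ratio.** With s0 and s1 the SDs at insertion and follow-up:
- Change score: s0² + s1² − 2·rho·s0·s1.
- Adjusted for insertion: s1²(1 − rho²).
- Ratio, adjusted to change: (1 − rho²)/(1 + lambda² − 2·rho·lambda).

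With equal SDs this is (1 + rho)/2. When rho = lambda it is 1, because the true slope rho/lambda is then 1 and nothing is gained.

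**Step 3: power with equal SDs.** The standardised difference becomes 0.50/√ratio, on 97 df.

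| rho | ratio | 0.50/√ratio | power | detectable at 80% (sd of change) |
|---|---|---|---|---|
| unadjusted | 1 | 0.500 | 69.7% | 0.566 |
| 0.25 | 0.625 | 0.632 | 87.9% | 0.447 |
| 0.5 | 0.75 | 0.577 | 81.5% | 0.490 |
| 0.7 | 0.85 | 0.542 | 76.6% | 0.522 |
| 0.9 | 0.95 | 0.513 | 71.9% | 0.552 |

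**Step 4: power when the insertion SD is smaller.** Every implant has the same target position: "After placement with the collar 1mm above the bone the insertion torque will be measured". That may narrow the insertion spread.

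| lambda | rho | ratio | power |
|---|---|---|---|
| 0.2 | 0.2 | 1.000 | 69.7% |
| 0.2 | 0.5 | 0.893 | 74.5% |
| 0.4 | 0.1 | 0.917 | 73.4% |
| 0.4 | 0.4 | 1.000 | 69.7% |
| 0.25 | 0.7 | 0.716 | 83.3% |

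Over lambda 0.2 to 0.4 and rho 0.1 to 0.5, the gain is 0 to about 5 points. A larger gain in this region needs a higher rho, as in the last row.

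**Step 5: the test SA-9 names.** Its meaning depends on the time levels, which are not listed.
- *Time is 12 and 24 months only.* The surface-by-time term compares collars on the 24-month minus the 12-month value, and the insertion reading cancels. In a fitted example with change as the response, the interaction was 0.274 (SE 0.204) with and without a baseline main effect, while the SE of the surface effect fell from 0.204 to 0.174. In simulation (50 per collar, all correlations 0.5, a 0.50 sd difference at both visits), this interaction test rejected about 5% of the time. The 24-month change comparison rejected about 70% unadjusted and 81% adjusted.
- *Insertion is also a time level.* The interaction then is a comparison of changes from insertion. With the same correlations and the same difference at both visits, the 2-df test has noncentrality 25 × 0.25 × (2/1.5) = 8.33 and about 72% power. The joint adjusted comparison has 25 × 0.25 × (2/1.0) = 12.5 and about 89% power.

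**The case against.** The strongest objection is that the power figures in 12.5 are for a t-test on change, whereas 12.4 names the surface-by-time interaction. This stands, and it shapes the remedy. Adding an insertion covariate and leaving the named test alone would do nothing for SA-9 if time means 12 and 24 months. If insertion was meant as a time level, moving it to a covariate without renaming the test would do harm: the test would stop asking about change since insertion and would have power near 5% for a constant collar difference.

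Second, SA-9 also compares extraction groups. For them the insertion film comes eight weeks after grafting, so grafting may already have altered the crest. If groups differ systematically at insertion, adjusted and unadjusted change estimate different quantities. This stands too: the adjustment belongs to the collar comparison only.

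Third, rho and the SD ratio are unknown, and the 1 mm target makes equal SDs doubtful. This stands as a limit on the size. It does not remove the case for adjusting, since the covariate costs at most two degrees of freedom even where it gains nothing.

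Fourth, 12.4 describes a general approach and does not forbid covariates. That is true, but leaving the choice open means it could be made after the data are seen.

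**Conclusion.** The point holds as a matter of precision. SA-9 works from change since insertion, the reading is scheduled at every implant, no adjustment for it is specified, and the stated 70% rests on the unadjusted SD of change.

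At 50 effective observations per collar, adjusting the collar contrast moves power from 69.7% to between about 72% and 88% for rho from 0.9 down to 0.25, if SDs are equal. It gives little or no gain wherever rho is close to the SD ratio. Which case applies cannot be settled from the documents.

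Three stronger readings are tempting, and the documents support none of them:
- *That the planned analysis is biased or invalid.* Unadjusted change is unbiased for a randomised collar comparison. Imbalance at insertion is a matter of chance.
- *That the trial would reach 82% power.* That figure needs rho = 0.5 and equal SDs, and neither is in the documents.
- *That a covariate alone repairs SA-9.* It does so only if the primary contrast is also restated.

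**What to change.** Amend SA-9 in 12.4 in three respects:

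1. **Model.** State that bone level at 12 and 24 months (or its change from insertion) is the response. Include the site's own insertion bone level and its interaction with visit as covariates, alongside smoking and the randomised factors. An equivalent is to keep insertion as a time level with its mean constrained to be equal across collars.
2. **Test of primary interest.** Replace the surface-by-time interaction with the LTT-RBT difference in change from insertion at 24 months, or jointly at 12 and 24 months.
3. **Scope.** Limit the adjustment to the collar comparison. Report the extraction-group comparisons as unadjusted change, from a model without the insertion covariate.

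The cost is a few sentences and one or two degrees of freedom. No new films, visits or participants are needed.
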